(e.g. glycemic variability); 2) the molecular and metabolic mechanisms by which unawareness leads to the suppression of CNS activity in the context of hypoglycemia; and 3) whether hypoglycemia avoidance using CGM restores CNS activation and metabolism toward normal levels and offers a therapeutic approach to more effectively combat neurocognitive dysfunction associated with intensive treatment of T1DM patients.

4. **Research Plan:** Summarize the study design and research procedures using non-technical language that can be readily understood by someone outside the discipline. **Be sure to distinguish between standard of care vs. research procedures when applicable, and include any flowcharts of visits specifying their individual times and lengths.** Describe the setting in which the research will take place.

Aim 1: Studies will be conducted in non-diabetic controls (N=25) and 2 groups of subjects with T1DM without significant complications: (1) hypoglycemia unaware (T1DM-UA) (N=40) and (2) hypoglycemia aware (T1DM-A) (N=25).

1. Screening visit: Volunteers will be screened at the Yale New Haven Hospital (YNHH) Hospital Research Unit (HRU) or the Yale Center for Clinical Investigation (YCCI) Church Street Research Unit (CSRU) with a medical history, physical exam, and EKG. Fasting blood work will be collected for A1C, ALT, TSH, electrolytes, renal function, CBC, and C-peptide. A urine pregnancy test will be performed on all women of childbearing potential, and women who are pregnant will be excluded.

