Data analysis will be conducted in collaboration with [name] at the Yale Center for Analytic Sciences. For Aim 1, we will require 25 T1DM aware and 25 healthy controls to provide 80% power to detect differences of 0.013 between them and the T1DM-Unaware subjects at the Bonferroni corrected 0.017 significance level. This sample size will also provide 80% power at the 0.01 level of significance to detect a difference of 0.22 for average brain glucose for Aim 2. We will enroll 27 aware and 27 healthy controls to accommodate a potential

5% inadequate scan rate. The T1DM Unaware group sample size (n=40) was first determined to provide sufficient power for Aim 3. T1DM Aware and healthy control sample sizes were then estimated based on power for aims 1 and 2. Our preliminary data shows differences in the co-primary outcome of average brain glucose between those with a low glucose variability index and those with a high glucose variability index of 0.455 (SD=0.26). We've also observed a difference of 0.013 (SD=0.016) in our other co-primary outcome change in brain activity from hypoglycemia to euglycemia in the striatum between T1DM Aware and Unaware. Thus, for Aim 3 a sample size of 20 T1DM Unaware subjects per arm will provide 80% power to detect a difference of 0.22 in brain glucose and 0.013 in change in brain activity. We will enroll 65 Unaware for Aim 3 in order to accommodate a potential 10% dropout rate.

Aim 1 Analysis: Comparison of brain activity between groups will be performed using a repeated measures mixed model. The outcome will be brain activity in our primary region of interest, the caudate region of the striatum. Fixed factors for group (unaware, aware, HC), glucose category (eugly, mild hypo, moderate hypo) and their interaction will be included. Linear contrasts comparing changes in brain activation from euglycemia to moderate hypo between groups will be estimated and evaluated at the 0.017 Bonferroni corrected significance level. Secondary analyses will examine other promising ROIs (hypothalamus and prefrontal cortex). Similar analyses will be done to assess group differences in resting state connectivity and hormones.

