Aim 2 Analysis: Comparisons of glucose levels in specific brain regions will be made using a repeated measures mixed model. Fixed factors include group and glycemic state (e.g. acute hyperglycemia) and their interaction. A random effect for subject will be used to accommodate correlation between repeated assessments. Linear contrasts comparing differences in average brain glucose between groups will be estimated. A significance level of 0.01 will be used to accommodate multiple pairwise comparisons of groups. Similar secondary analyses will be conducted to assess differences in V_{TCA} between groups and fructose production during hyperglycemia. For the rodent studies our preliminary data showed a 1.5 standardized difference in fructose and glutathione concentrations between groups, so a sample size of 14-15 rats per group will provide 80% power to detect a large standardized difference in study outcomes at the two-sided 0.05 significance level. Between-group comparisons, ANOVA and t-tests will be used for continuous variables, where applicable.

Plan for Missing Data: Prevention is the obvious way to control for bias and loss of power from missing data (71). We will follow the intent to treat principle, requiring follow-up of all subjects regardless of treatment³⁴. Postcard and telephone visit reminders will be sent and alternative contacts identified to minimize loss to follow-up. Timely data entry and weekly missing data reports will trigger protocols for obtaining missing data items. Despite these efforts it is reasonable to assume missing data will occur most likely at random³⁵. We will evaluate the plausibility of this assumption using logistic regression to identify factors linked to dropout.

SECTION II: RESEARCH INVOLVING DRUGS, BIOLOGICS, RADIOTRACERS, PLACEBOS AND DEVICES

If this section (or one of its parts, A or B) is not applicable, check off N/A and delete the rest of the section.

A. RADIOTRACERS N/A

B. DRUGS/BIOLOGICS N/A

1. Use of Placebo: Not applicable to this research project

2. Continuation of Drug Therapy After Study Closure Not applicable to this project

B. DEVICES N/A

1. Are there any investigational devices used or investigational procedures performed at Yale-New Haven Hospital (YNHH) (e.g., in the YNHH Operating Room or YNHH Heart and Vascular Center)? Yes No

If Yes, please be aware of the following requirements:

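### Section 13 enrols 65 Unaware subjects to cover 10% dropout from a group of 40, but that allowance gives 45

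*Combined protocol and SAP*

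**What the plan says.** Section 13 fixes the Unaware group before the other two: "The T1DM Unaware group sample size (n=40) was first determined to provide sufficient power for Aim 3". It explains the 40 as two arms of 20: "for Aim 3 a sample size of 20 T1DM Unaware subjects per arm will provide 80% power to detect a difference of 0.22". That difference refers to brain glucose, and a matching statement covers brain activity. The enrolment target then follows: "We will enroll 65 Unaware for Aim 3 in order to accommodate a potential 10% dropout rate".

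Earlier in the same paragraph the two comparison groups are inflated from 25 each: "We will enroll 27 aware and 27 healthy controls to accommodate a potential". The allowance there is for inadequate scans, at a rate of 5%.

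Elsewhere in the protocol:

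- Section 4 (Research Plan), Aim 1, lists the diabetes groups as "1) hypoglycemia unaware (T1DM-UA) (N=40) and (2) hypoglycemia aware (T1DM-A) (N=25", plus 25 controls. The Optional Sub Study repeats the 40 and 25.
- Section 4, Aim 3, item 1 places 40 Unaware subjects on a single real-time glucose monitor, with no second arm described. Item 4 nevertheless mentions a Group 2.
- Section 6 (Subject Population) gives 65 subjects with type 1 diabetes and 25 controls.
- Section III gives a site target of 150 in item 1, and about 65 subjects in the recruitment message.

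**The concern.** The only reason offered for 65 is a 10% dropout rate, yet 65 is more than 60% above the 40 it starts from. No other margin, such as screen failure or unusable scans, is mentioned for this group.

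This sentence is the only place where the Unaware sample size becomes an enrolment target that allows for losses, and all three aims use the Unaware group. A study team or ethics board reading Section 13 would take the target to be 65. Reading Section 4, they would take it to be 40, which has no allowance for dropout if 40 is the number enrolled. The text does not say which applies.

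**Working it through.** **Inputs.** Unaware group 40, as 20 per arm; Aim 3 dropout 10%; stated Unaware enrolment 65; comparison groups 25 each, inadequate scans 5%, stated enrolment 27 each (all Section 13). Diabetes groups 40 and 25 (Section 4). Diabetes total 65 (Section 6).

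**Formula.** Number enrolled = number evaluable / (1 − loss rate), rounded up.

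**Step 1: the plan's own figure that works.** Comparison groups: 25 / (1 − 0.05) = 26.3, so 27. This matches, so the paragraph uses the ordinary inflation.

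**Step 2: the same formula for the Unaware group.** 40 / (1 − 0.10) = 44.4, so 45.

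**Step 3: other conventions.**

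| Method | Arithmetic | Enrolled |
|---|---|---|
| Divide by the retained fraction | 40 / 0.9 = 44.4 | 45 |
| Multiply by 1 + rate | 40 × 1.1 | 44 |
| Round up each arm | 20 / 0.9 = 22.2, so 23; 2 × 23 | 46 |
| Stated in Section 13 | – | 65 |

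**Step 4: what 65 would mean.** Loss needed to end at 40: 1 − 40/65 = 0.385, or 38.5%. Completers from 65 at 10% loss: 65 × 0.9 = 58.5, so about 58. Excess over 45: 65 − 45 = 20, and 65/45 = 1.44, or 44% over.

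**Step 5: where 65 may come from.** 40 + 25 = 65, the diabetes total in Section 6. On that reading 65 is the sum of the two groups before any inflation, so it contains no dropout allowance.

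**Step 6: whether the other totals settle it.** 65 + 27 + 27 = 119 and 45 + 27 + 27 = 99. Both lie below the site target of 150, so that target does not distinguish them.

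**Step 7: if 40 is the number enrolled.** 40 × 0.9 = 36 evaluable in Aim 3, below the 40 on which the 80% power statement rests.

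**The case against.** The best defence is that 65 is a slip with little practical effect. If it is the diabetes total in the wrong sentence, nobody intends to enrol 65 Unaware subjects, the design sections already use 40, and 119 participants would still fit within 150. This bears on the likely consequence but does not rescue the number. It also leaves the plan without a working dropout allowance for this group.

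A second objection stands: 45 is not automatically the right replacement. It assumes that 40 means evaluable subjects and that the 20-per-arm basis still holds, while Section 4 describes one monitoring group. The mismatch needs no assumption; the replacement does.

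Two stronger readings are tempting and should not be drawn.

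- *Twenty extra people would undergo hypoglycemic clamps.* Section 4, Aim 1 (hypoglycemia questionnaires) classifies awareness partly from questionnaires and hormones collected during the fMRI clamp. Exposure to the first clamp therefore depends on total diabetes enrolment and on how subjects classify, not on the Unaware target alone.
- *The Aim 2 power is also wrong.* Section 13 says: "This sample size will also provide 80% power at the 0.01 level of significance to detect a difference of 0.22" in average brain glucose. It ties no SD to that contrast and does not state whether the human tests are one- or two-sided. The only brain-glucose SD, 0.26, comes from groups with low and high glucose variability. If it is borrowed for a simple two-sample comparison of 40 with 25, power is 74–77% two-sided and 82–84% one-sided (t to normal approximation), so the answer turns on what is unstated. The planned mixed model could change it again. Nor does the paragraph explicitly claim 80% for Aware against controls: its Aim 1 power statement concerns differences from the Unaware group, and the Aim 2 sentence follows from it.

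**Conclusion.** The enrolment figure is wrong as written. With 40 as the base and 10% dropout, the target is 45 (44 to 46 by convention), and 65 exceeds 45 by 20 subjects. Confidence in the mismatch is high, since it uses only figures printed in Section 13. That 65 is the misplaced diabetes total is probable but remains an inference. The choice of 45 is conditional on 40 being the evaluable target. Nothing here shows that any stated power is wrong; the missing Aim 2 SD and sidedness are at most a minor request for clarification.

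**What to change.** 1. Confirm that 40 is still the evaluable Unaware target, reconciling the two arms of 20 in Section 13 with the single monitoring group in Section 4, Aim 3.
2. Then either replace 65 with 45 enrolled for 40 evaluable, or keep 40 enrolled, state that about 36 will be evaluable after 10% dropout, and restate the Aim 3 power on that number. Section 13 gives no significance level for Aim 3, so the restatement should name one.
3. Carry the same Unaware number through Section 4 (Aim 1, Aim 3 and the Optional Sub Study), Section 6 and Section 13, marking each count as enrolled or evaluable. With 45 Unaware and 27 Aware enrolled, the diabetes total is 45 + 27 = 72 enrolled, against 40 + 25 = 65 evaluable.
4. As a minor clarification, state the SD and sidedness behind the Aim 2 power figure.

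The cost is small. Enrolling 45 is 20 fewer than Section 13 now says and 5 more than Section 4. Keeping 40 enrolled adds nobody but leaves fewer completers. Item 4 is wording only.

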After 14 days of wearing the CGM, it will be removed by a trained study staff member. To remove the sensor, the adhesive patch will be gently peeled off from the skin, together with the sensor. Removal of the sensor is a painless procedure. The sensor will be discarded after use.

Note regarding order of visits: CGM placement will occur up to 14 days prior to the subject's first scan (fMRI or MRS). CGM removal will occur on the same day as the subject's first scan (fMRI or MRS). Due to the many complexities of scheduling, although the fMRI is part of Aim 1, the subject may have the MRS scan done first, which is part of Aim 2. The order of scans in no way effects subject safety or research integrity. T1DM subjects will have a second CGM placed after the first scan and will wear this CGM until the second scan, where it will be removed. Therefore, T1DM subjects will wear the CGM two times, once before each scan for up to 14 days prior.

4. fMRI Scan with hyperinsulinemic euglycemia-mild hypoglycemia clamp: All subjects will arrive on the morning of the scan at 7AM following an 8-hr fast. T1DM subjects will be instructed to continue their home insulin regimen until they arrive at the Yale Magnetic Resonance Research Center (MRRC) that is equipped with infusion rooms for IV and line placements. A urine pregnancy test will be performed on all women of childbearing potential, and women who are pregnant will be excluded. Following IV placements and baseline blood collections at ~8 AM subjects will receive an insulin infusion (2 mU/kg/min) together with a variable glucose infusion to keep glucose levels at ~100-110 mg/dl. Once glucose levels are stabilized outside the magnet (~45 min), they will be transferred into the MRI for a 2-step hyperinsulinemic euglycemic (90-100 mg/dl)-mild hypoglycemic (55-60 mg/dl) clamp. Initially, baseline structural scans will be obtained, followed by blood oxygen level dependent (BOLD) contrast acquisitions during visual cues and cognitive tasks. At each clamp step, participants will also be asked to complete questionnaires assessing hypoglycemia. Plasma glucose will be measured every 5-10 min. Throughout, blood will be obtained for insulin, glucagon, cortisol, catecholamines and other hormonal and metabolic blood tests. A1c will also be measured at this visit.

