4. Repeat brain MRS and fMRI scans: At 12 weeks, all subjects will repeat fMRI and MRS analyses of brain glucose transport/metabolism under hypo- and hyperglycemia exactly as described in Aims 1 and 2. At 12 weeks, the subjects in Group 2 will repeat fMRI and MRS analyses of brain glucose transport/metabolism under hypo- and hyperglycemia exactly as described in Aims 1 and 2. A1c will also be measured at all scan visits. Hypoglycemia questionnaires will also be repeated, in addition to repeat cognitive assessments (using different test versions to reduce practice effects).

Note regarding order of visits: As is the case in Aims 1 and 2, CGM placement will occur up to 14 days prior to the subject's first scan of Aim 3 (fMRI or MRS). CGM removal will occur on the same day as the subject's first scan of Aim 3 (fMRI or MRS). Due to the many complexities of scheduling, there is no order that the fMRI and MRS must be performed. The order of scans in no way effects subject safety or research integrity.

Optional Sub Study: Subjects from Aim 1 and 2 with T1DM: (1) hypoglycemia unaware (T1DM-UA) (N=40) and (2) hypoglycemia aware (T1DM-A) (N=25) will be given the opportunity to participate in this optional sub study. We will only contact those previously enrolled participants who agreed to be re-contacted for future research by indicating such on the AIM 1 and 2 consent form.

1. Consenting: Subjects will be consented for this optional Sub study through the Qualtrics study link. The consent form will be provided as a study question. Subject will either click yes or no to agreeing to completed issued questionnaires. If subject, clicks yes and provides name and date, questions from survey will be provided. If subject clicks no, subject will not be provided additional questionnaires.
2. Subject Contact: Only subjects with T1DM and already eligible to participate in Aim 1 and Aim 2 will be contacted via telephone and explained the purpose of the sub-study.
3. Diabetes and health status questionnaires: All participants who agree to participate will be asked to complete questionnaires (all standard, well-validated questionnaires) for assessing hypoglycemia, self-evaluate their diabetes healthcare, general stress and anxiety during the COVID-19 pandemic and unprecedented stay-at-home experience. Questionnaires include:
 - a. Clarke, Gold, Pedersen : Classifies awareness of hypoglycemia, three different measures

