The infusion of insulin and glucose to achieve hypoglycemia will potentially result in symptoms of varying severity. Some subjects will experience little or no symptoms of sleepiness, hunger, anxiety, palpitations, diaphoresis, difficulty concentrating, mild confusion and/or tremor. There is a small risk that plasma glucose will fall below the predetermined level (3.0-3.5 mM, 55-60 mg/dl) resulting in exaggerated symptoms. All such symptoms would be rapidly reversible with an intravenous dextrose infusion.

The infusion of glucose to achieve hyperglycemia (~180 mg/dl) is not associated with any specific symptoms or significant adverse effects. This modestly high glucose level can be seen in poorly controlled diabetic patients following a meal.

¹³C glucose:

The infusion of ¹³C glucose involves no radioactivity, and the glucose is metabolized just as unlabeled glucose. Clinical research studies using ¹³C glucose have been used at Yale for decades with no adverse effects. The glucose solution is purchased from (Cambridge Isotopes, Inc.) in powder form which has been certified to be sterile and free of pyrogens. The glucose is made into a solution of 20gram/100 ml (D-20) by the Yale New Haven Hospital Investigational Drug Service (IDS). The solutions are tested to be free of pyrogens and to be sterile before being administered. All certifications are kept with the IDS.

MRI/MRS:

Magnetic resonance (MR) is a technique that uses magnetism and radio waves, not x- rays, to take pictures and measure chemicals of different parts of the body. The United States Food and Drug Administration (FDA) has set guidelines for magnet strength and exposure to radio waves, and we carefully observe those guidelines.

A member of our research staff will accompany the subject to the MRRC and remain there for the scan. The subject will be watched closely throughout the MR study. Some people may feel uncomfortable or anxious. If this happens to the subject, they may ask to stop the study at any time and we will take them out of the MR scanner. On rare occasions, some people might feel dizzy, get an upset stomach, have a metallic taste or feel tingling sensations or muscle twitches. These sensations usually go away quickly but we will instruct the subject to tell the research staff if they have them.

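### Aim 1's primary contrast uses a 'moderate hypo' level that the described fMRI clamp does not schedule

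*Combined protocol and SAP*

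**What the plan says.** **Analysis text (Section I, item 13, Aim 1 Analysis).** The outcome is activity in the caudate, analysed with a repeated measures mixed model. The fixed factors are group (unaware, aware, healthy control) and "glucose category (eugly, mild hypo, moderate hypo) and their interaction will be included". The only contrast specified for this primary region is: "Linear contrasts comparing changes in brain activation from euglycemia to moderate hypo between groups will be estimated". It is tested at a Bonferroni-corrected 0.017. Other regions are secondary, and connectivity and hormones are to be analysed similarly.

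**Sample size text (same item).** The outcome is described without a depth of hypoglycemia: "our other co-primary outcome change in brain activity from hypoglycemia to euglycemia in the striatum between T1DM Aware and Unaware". The planning effect is 0.013 with SD 0.016.

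**Procedure (Section I, item 4, Aim 1, step 4).** The step is headed "fMRI Scan with hyperinsulinemic euglycemia-mild hypoglycemia clamp". Glucose is first held at about 100-110 mg/dl before scanning: "Once glucose levels are stabilized outside the magnet (~45 min), they will be transferred into the MRI". What follows in the scanner is a "2-step hyperinsulinemic euglycemic (90-100 mg/dl)-mild hypoglycemic (55-60 mg/dl) clamp".

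**Risks (Section I, item 10, insulin and glucose infusion).** One target level is given, and lower glucose is described as an unintended event: "There is a small risk that plasma glucose will fall below the predetermined level (3.0-3.5 mM, 55-60 mg/dl) resulting in exaggerated symptoms".

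**Aim 3 repeat scans (Section I, item 4, Aim 3, step 4).** The procedure is carried over unchanged: "all subjects will repeat fMRI and MRS analyses of brain glucose transport/metabolism under hypo- and hyperglycemia exactly as described in Aims 1 and 2".

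**The concern.** The model has two hypoglycemic categories and the clamp has one hypoglycemic step. The category that carries the primary contrast is the one the procedure never mentions. No section available for review defines 'moderate hypo' by a glucose range, schedules a scan at it, or says that categories will be assigned from the glucose each subject actually reached.

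This is the stated confirmatory rule for a co-primary outcome, and it affects all three Bonferroni-adjusted group comparisons. If the text stays as it is, someone will have to reword the contrast or choose achieved-glucose cut-points once the data are in hand. Under the second route, a deeper category would be filled only by departures from the clamp target, with boundaries that were not fixed in advance.

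A smaller point follows. The plan does not say which glycemic step produced the 0.013 planning effect, so a reader cannot confirm that it refers to the step that will be scanned.

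**Working it through.** **1. The plan's own power figure.** Inputs from item 13: difference 0.013, SD 0.016, 40 unaware against 25 aware (or 25 controls), level 0.017 (0.05/3 = 0.0167 for three group pairs). Sidedness is not stated; two-sided is assumed.

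- Standard error = 0.016 × √(1/40 + 1/25) = 0.016 × √0.065 = 0.00408.
- Difference / standard error = 0.013 / 0.00408 = 3.187.
- Critical value z(1 − 0.0085) = 2.387.
- Power = Φ(3.187 − 2.387) = Φ(0.800) = 78.8%. The noncentral t with 63 degrees of freedom gives 76.7%.

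The stated 80% is approximately reproduced. It does not depend on what the hypoglycemic step is called, provided the effect belongs to the step that is scanned.

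**2. Categories against scanned steps.**

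| Model category (item 13) | Scanned step (item 4) | Range given |
|---|---|---|
| eugly | euglycemic step | 90-100 mg/dl |
| mild hypo | hypoglycemic step, called mild | 55-60 mg/dl |
| moderate hypo | none | none |

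The holding period at about 100-110 mg/dl is outside the magnet, so it is not a third scanned level.

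**3. Estimability.** Write μ(g,k) for the mean in group g and glucose category k: 3 × 3 = 9 cell means. The procedure yields 40 + 25 + 25 = 90 subjects × 2 scanned steps = 180 rows. The named contrast for groups a and b is

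[μ(a,mod) − μ(a,eu)] − [μ(b,mod) − μ(b,eu)].

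It is estimable only if its coefficient vector lies in the row space of the design matrix, that is, if adding it as a row does not raise the rank.

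| Labels of the two scanned steps | Rank (of 9) | Euglycemia to moderate | Euglycemia to mild |
|---|---|---|---|
| eugly and mild hypo (as item 4 names them) | 6 | 0 of 3 pairs | 3 of 3 pairs |
| eugly and moderate hypo (if 'moderate' means 55-60 mg/dl) | 6 | 3 of 3 pairs | 0 of 3 pairs |

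In each row one category has no scheduled observations, so three of the nine means are unidentified. A random subject effect does not change this, because it cannot supply the fixed effect of a level that is never observed.

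**4. Why the origin of the planning effect should be stated.** This is an illustration only; the documents do not say that 0.013 came from a deeper level. Suppose it did, and the effect at the scanned step were 90%, 75% or 50% of it with the same SD. The normal-approximation power would be 68.5%, 50.1% or 21.4%.

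**The case against.** The strongest reply is that this is a labelling slip. If 'moderate hypo' simply means the 55-60 mg/dl step, the contrast can be run for every pair and the only fault is an unused factor level. The outcome is also worded without depth in the sample size text, and region, group comparisons, model type and significance level are all fixed. With a single scheduled hypoglycemic step there is no second scheduled contrast for an analyst to choose. The rank calculation restates the mismatch and cannot show which reading was intended. The source of 0.013 is a missing detail, not a demonstrated error.

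Much of this stands. The outcome is not lost, non-estimability depends on the reading, and rewording the contrast to the scanned step would follow the depth-free outcome definition. The supporting sections also carry limited weight: only item 4 uses the word mild, item 10 supports a single level without grading it, and the Aim 3 text only refers back. Item 10's own units differ slightly, since 3.0-3.5 mM × 18.016 is about 54-63 mg/dl, so the agreement is in the mg/dl figures.

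The reply does not remove the need for a correction. Item 13 lists mild and moderate as separate levels of one factor, so within the model they are not synonyms. On the labelling reading, item 13 calls moderate what item 4 calls mild. And a contrast reworded after the data are in hand is still a change to the stated primary rule.

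**Conclusion.** The concern holds and should be corrected before analysis. The stated primary contrast for an Aim 1 co-primary outcome does not match the data the clamp will produce. Taking the labels as written, it is estimable for 0 of 3 group pairs; if 'moderate hypo' is a second name for the scanned step, it is estimable for 3 of 3 and 'mild hypo' has no scheduled observations. A correction is needed on both readings.

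Confidence in the textual mismatch is high. Which reading was intended cannot be settled from the documents. The conclusion assumes that nothing in the small part of the recruitment section missing from the review copy defines the category. The 80% power is not challenged, and no view is taken on which glucose target is right.

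**What to change.** Before analysis, reconcile item 13 with items 4 and 10, and give every modelled glucose category a range that corresponds to a scanned step.

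- If the procedure text is current: use a two-level glucose factor, and define the primary contrast as the between-group difference in change from the euglycemic step to the scanned hypoglycemic step, in the caudate, at 0.017.
- If the analysis text is current: the procedure and risk sections must be brought into agreement with it.
- In either case: state which glycemic step the 0.013 (SD 0.016) effect came from.

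In the first case the cost is low: only the model and contrast wording in item 13 changes, with no effect on sample size. In the second it is more than wording, because the description of the procedure and its risks is also affected.
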